8.1 Assessment schedule

Subjects should be seen for all visits/assessments as outlined in the assessment schedule or as close to the designated day/time as possible. The assessment schedule is applicable for both Part 1 and 2 of the study.

Missed or rescheduled visits should not lead to automatic discontinuation. Subjects who prematurely discontinue the study for any reason should be scheduled for a visit as soon as possible, at which time all of the assessments listed for the final visit will be performed. At this final visit, all dispensed investigational product should be reconciled, and the adverse event and concomitant medications recorded on the CRF.

Table 8-1 Assessment Schedule for Part 1 of the Study

Period	Screening		Treatment														Safety Follow Up	EOS		
Visit Name	Screening	Baseline	Treatment																	
Visit Numbers ¹	1	20	110			120		130	140						150	160	170	1999		
Days	run-in phase	-7 to -4	1			8 ±1		15±2	30 ±3						60±3	90±3 ¹⁵	120±5	180±5		
Time (post-dose)	-	-	Pre-dose	1h	2h	Pre-dose	1h	-	Pre-dose	0.25h	0.5h	1h	2h	4h	6h	8h	-	-	-	-
Informed consent	X																			
Inclusion / Exclusion criteria	X	X																		
Vaccination	X																			
Medical history/current medical conditions	X																			
Pregnancy and assessments of fertility ¹⁴	S	S						S									S	S		S

Period	Screening		Treatment																Safety Follow Up	EOS		
Visit Name	Screening	Baseline	Treatment																			
Visit Numbers ¹	1	20	110				120				130				140				150	160	170	1999
Days	run-in phase	-7 to -4	1				8 ±1				15±2				30 ±3				60±3	90±3 ¹⁵	120±5	180±5
Time (post-dose)	-	-	Pre-dose	1h	2h	Pre-dose	1h	-	Pre-dose	0.25h	0.5h	1h	2h	4h	6h	8h	-	-	-	-		
Hepatitis and HIV Screen	S																					
Demography	X																					
Pulse rate ²	X	X	X	X	X	X	X	X	X				X				X	X	X	X		
Blood Pressure ²	X	X	X	X	X	X	X	X	X				X				X	X	X	X		
Body Temperature ²	X	X	X			X		X	X								X	X	X	X		
Physical Examination ²	S	S						S										S	S	S		
Body Height	X																					
Body Weight	X	X	X			X		X	X								X	X				
Electrocardiogram (ECG)	X	X	X	X			X	X	X				X				X	X				
Alcohol Test and Drug Screen	S	S																				
24h urine collection ³	X ¹⁸	X							X									X				
First morning void urine (midstream) ⁴	X	X	X			X		X	X								X	X	X	X		
Estimated Glomerular filtration rate ⁵	X	X	X			X		X	X									X	X			
Hematology ²	X	X	X			X		X	X								X	X	X			

[figure not shown]
Period	Screening		Treatment														Safety Follow Up	EOS		

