Visit Name	Screening	Baseline	Treatment																	
Visit Numbers ¹	1	20	110			120		130	140						150	160	170	1999		
Days	run-in phase	-7 to -4	1			8 ±1		15±2	30 ±3						60±3	90±3 ¹⁵	120±5	180±5		
Time (post-dose)	-	-	Pre-dose	1h	2h	Pre-dose	1h	-	Pre-dose	0.25h	0.5h	1h	2h	4h	6h	8h	-	-	-	-
Clinical Chemistry ^{2,7}	X	X ¹⁷	X			X		X	X								X	X ¹⁷	X	X
PK blood collection						X		X ¹⁶	X	X	X	X	X	X	X	X	X ¹⁶	X ¹⁶		
blood levels of testosterone, FSH, LH, DHT and thyroid hormones ⁶		X						X	X								X	X		X
Safety Urinalysis ^{2,13}	X	X	X			X		X	X								X	X	X	X
PD 		X				X		X	X							X	X	X		

Table 8-2 Assessment Schedule for Part 2 of the Study

Period	Screening		Treatment														Safety Follow Up	EOS
	Visit Name	Screening	Baseline															
Visit Numbers ¹	1	20	110	120	130	140						150	160	175	180	190	2999	
Days	run-in phase	-7 to -4	1	8±1	15±2	30 ± 3						60±3	90±3 ¹⁵	135±7	180±7 ¹⁵	210±7	270±7 ¹⁵	
Time (post-dose)	-	-	Pre-dose	1h	-	-	Pre-dose	0.25 h	0.5 h	1h	2h	4h	6h	8h	-	-	-	-
Informed consent	X																	
Inclusion / Exclusion criteria	X	X																
Vaccination	X																	
Medical history/current medical conditions	X																	
Pregnancy and assessments of fertility ¹⁴	S	S					S								S	S		S
Hepatitis and HIV Screen	S																	
Demography	X																	
Pulse rate ²	X	X	X	X	X	X	X				X				X	X	X	X
Blood Pressure ²	X	X	X	X	X	X	X				X				X	X	X	X

Period	Screening		Treatment														Safety Follow Up	EOS		
	Visit Name	Screening	Baseline																	
Visit Numbers ¹	1	20	110	120	130	140						150	160	175	180	190	2999			
Days	run-in phase	-7 to -4	1	8±1	15±2	30 ± 3						60±3	90±3 ¹⁵	135±7	180±7 ¹⁵	210±7	270±7 ¹⁵			
Time (post-dose)	-	-	Pre-dose	1h	-	-	Pre-dose	0.25 h	0.5 h	1h	2h	4h	6h	8h	-	-	-	-		
Body Temperature ²	X	X	X		X	X	X								X	X	X	X	X	X
Physical Examination ^{2, 20}	S	S				S										S	S	S	S	S
Body Height	X																			
Body Weight	X	X	X		X	X	X								X	X	X	X		
Electrocardiogram (ECG) ²	X	X	X	X		X	X				X				X	X	X	X		
Alcohol Test and Drug Screen	S	S																		
24h urine collection ³	(X) ¹⁸	X					X									X		X		
First morning void urine (midstream) ⁴	(X) ¹⁸	X	X		X	X	X								X	X	X	X	X	X
Estimated Glomerular filtration rate ⁵	X	X	X		X	X	X								X	X	X	X	X	X
Hematology ^{2, 21}	X	X	X		X	X	X								X	X	X	X	X	X

Period	Screening		Treatment														Safety Follow Up	EOS		
	Visit Name	Screening	Baseline																	

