Visit Numbers ¹	1	20	110	120	130	140						150	160	175	180	190	2999			
Days	run-in phase	-7 to -4	1	8±1	15±2	30 ± 3						60±3	90±3 ¹⁵	135±7	180±7 ¹⁵	210±7	270±7 ¹⁵			
Time (post-dose)	-	-	Pre-dose	1h	-	-	Pre-dose	0.25 h	0.5 h	1h	2h	4h	6h	8h	-	-	-	-		
Clinical Chemistry ^{2,7}	X	X ¹⁷	X		X	X	X								X	X ¹⁷	X	X ¹⁷	X	X
PK blood collection					X ¹⁶	X ¹⁶	X	X	X	X	X	X	X	X	X ¹⁶	X ¹⁶	X ¹⁶	X ¹⁶		
blood levels of testosterone, FSH, LH, DHT and thyroid hormones ⁶		X				X	X								X	X	X	X		X
Safety Urinalysis ^{2, 13, 19}	X	X	X		X	X	X								X	X	X	X	X	X

¹ Visit structure given for internal programming purpose only

² Unless specified otherwise, these procedures, including infection surveillance, are performed before the morning dose (i.e. predose) at each visit

³ The 24hour urine collection should start one day prior to the clinic visit, **AFTER** the patient urinates for the first time, then all urine in the next 24 hours will be collected and refrigerated before being taken to the clinic. Assessments may include but not limited to UACR and UPCR, 24h urine excretion of albumin and protein, renal function biomarkers, PK (except at Baseline)

⁴ A midstream urine sample will be obtained from the first morning void (FMV) on the visit day. For Visits 20, 140, 160 and 180 when both FMV and 24-hour urine samples are required, FMV should be collected one day prior to the clinic visit. The collected urine sample should be refrigerated before being taken to the clinic. Assessments may include but not limited to UACR and UPCR, renal function biomarkers.

⁵ Estimated Glomerular Filtration Rate (eGFR) is calculated according to CKD-EPI. Modified MDRD formula according to specific ethnic groups and local practice guidelines (Imai et al 2011) may be used at Visit 1 only.

⁶ including thyroid function surveillance (T3, reversed T3, T4, Thyroid Stimulating Hormone - TSH-DHT level assessment)

⁷ Clinical chemistry includes total protein, albumin, creatinine, glucose, sodium, potassium, lipids, and liver safety monitoring (ALT, AST, ALP, TBL, PT/INR, GGT levels assessment) etc.

⁸ [REDACTED]
⁹ May include but not limited to sC5b-9, Bb, [REDACTED]

¹¹ LNP023 to be administered b.i.d. daily from Day 1 to Day 90 in Part 1, Day 1 to Day 180 in Part 2. At days of the study visit, the morning dose of study medication will be administered at the study center after pre-dose sampling, evening dose can be taken at home.

¹² [REDACTED]
¹³ [REDACTED]

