7.2.1 Variables

The secondary variables are the following:

- Log ratio to baseline in UPCr (from 24hr urine up to Day 180)
- Log ratio to baseline in UPCr (from first morning void)
- Change from baseline in eGFR
- Change from baseline in Serum Creatinine

- Hematuria
- Log ratio to baseline in 24h-UP.
- Log ratio to baseline in 24h-UA
- Log ratio to baseline in UACR

The 24h-UP and 24h-UA will be derived using the following formula:

$$\text{True 24h parameter} = \frac{(\text{measured parameter content} \times 24)}{\text{length of time (in hour) sample collected over}}$$

Baseline is defined to be the last measurement prior to the start of study drug administration. Each secondary variable is derived from the 24h urine collections at baseline, day 30 and 90, except for the eGFR and Serum Creatinine which are derived from the blood measurements at baseline, day 1, 8, 15, 30 and 90 and UPCR and hematuria which are derived from FMV samples at baseline, day 1, 8, 15, 30, 60 and 90. For analyses on FAS2, measurements up to day 180 will be considered (additionally day 60 and 135 for eGFR and Serum Creatinine).

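### The pooled Day-90 models for serum creatinine and eGFR leave out Day 60, although creatinine is scheduled at Day 60 in both parts

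*SAP*

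**What the plan says.** **Visit lists.** SAP 7.2.1 defines the visits for the secondary variables. For the pooled analysis (FAS to Day 90) it specifies "eGFR and Serum Creatinine which are derived from the blood measurements at baseline, day 1, 8, 15, 30 and 90". The same sentence keeps Day 60 for the first-morning-void variables: "UPCR and hematuria which are derived from FMV samples at baseline, day 1, 8, 15, 30, 60 and 90". For FAS2, the Part 2 patients on 180 days of treatment, the SAP extends the list: "additionally day 60 and 135 for eGFR and Serum Creatinine". It gives no reason for the difference.

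**Schedule.** In Protocol 8.1, the clinical chemistry rows of Table 8-1 (Part 1) and Table 8-2 (Part 2) are both marked at Day 60. Footnote 7 confirms the content: "Clinical chemistry includes total protein, albumin, creatinine, glucose, sodium, potassium, lipids, and liver safety monitoring". The eGFR row is marked at Day 60 in Table 8-2 but not in Table 8-1. Footnote 5 reads "Estimated Glomerular Filtration Rate (eGFR) is calculated according to CKD-EPI". Protocol 8.5.3 gives the equation, whose inputs are serum creatinine, age, sex and race.

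**Model and status.** SAP 7.2.3 fits each secondary variable except hematuria with an MMRM like the primary one. SAP 7.1.3.1 justifies the primary MMRM by a missing-at-random assumption, conditional on observed responses and covariates. The introduction to SAP section 7 declares the pooled Day-90 eGFR and creatinine analyses final at IA2, with a re-run only if later data discrepancies are judged to matter.

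**The concern.** An MMRM can adjust for dropout only through values that are in the model. If a patient attends Day 60, shows a worse creatinine, and then has no usable Day-90 value, the pooled model predicts that patient's Day 90 from Day 30 and earlier. The value that may explain the dropout is left out, although the schedule provides for it.

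The documents offer two plausible routes to this pattern:

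- Protocol 7.2 lists laboratory abnormalities, on the investigator's judgement, among the reasons for stopping study treatment. The primary analysis uses data only up to treatment discontinuation. If the secondary models follow that rule, a patient who stops after Day 60 contributes no Day-90 value even if seen.
- Protocol 3.5 and SAP section 3 treat Day-90 visits after the IA2 cutoff as missing. That adds patients with Day 60 but no Day 90, although not necessarily for reasons linked to renal function.

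At stake is the estimate of renal function at Day 90 across both parts, a stated secondary objective (Protocol 2.2). The direction matters: selective loss of patients with poor Day-60 values would make the arm's eGFR look better, and its creatinine lower, than it is.

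**Working it through.** The plan has no figure to reproduce: Protocol 11.8 does not assess power for secondary variables, and the documents give no SD or between-visit correlation for eGFR.

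**Step 1. On-treatment visits to Day 90, set side by side (column count of the tables)**

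| Source | Visits |
|---|---|
| Table 8-1 chemistry (Part 1) | 1, 8, 15, 30, 60, 90 |
| Table 8-2 chemistry (Part 2) | 1, 8, 15, 30, 60, 90 |
| Table 8-1 eGFR (Part 1) | 1, 8, 15, 30, 90 |
| Table 8-2 eGFR (Part 2) | 1, 8, 15, 30, 60, 90 |
| SAP 7.2.1 pooled eGFR and creatinine | 1, 8, 15, 30, 90 |

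Day-60 creatinine is scheduled for all patients and unused in the pooled models. Day-60 eGFR is scheduled in Part 2 and used for FAS2, but dropped from the pooled model.

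**Step 2. Bias under selective dropout**

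Assumptions: normal changes from baseline; SD 8 mL/min; Day 90 missing for the fraction p of one arm with the lowest Day-60 values; Days 1, 8, 15 and 30 in the model. Let c be the p-quantile of the standard normal, λ = φ(c)/(1−p) and δ = λ(λ−c).

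- p = 0.10: c = −1.2816, λ = 0.195, δ = 0.288.
- p = 0.20: c = −0.8416, λ = 0.350, δ = 0.417.

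*AR(1), correlation ρ per 30 days.* Only Day 30 carries information among the earlier visits.

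Bias = 8·λρ(1−ρ²)/(1−ρ²δ)

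Example, ρ = 0.7 and p = 0.20: 8 × 0.350 × 0.7 × 0.51 / (1 − 0.49 × 0.417) = 1.26.

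*Compound symmetry, correlation ρ.* The mean of the four earlier visits has variance v = (1+3ρ)/4 in SD² units.

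Bias = 8·λρ(v−ρ)/(v−ρ²δ)

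Example, ρ = 0.5 and p = 0.20: 8 × 0.350 × 0.5 × 0.125 / (0.625 − 0.25 × 0.417) = 0.34.

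| Bias in Day-90 mean, mL/min, ρ = 0.5 to 0.8 | p = 0.10 | p = 0.20 |
|---|---|---|
| AR(1) | 0.55 to 0.67 | 1.10 to 1.28 |
| Compound symmetry | 0.09 to 0.18 | 0.19 to 0.34 |

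Simulation of the full visit set agrees with these values and gives about 0 in every case once Day 60 is added. With graded dropout instead (odds doubling per SD lower at Day 60, same overall fractions), the bias is about 0.15 to 0.4 under AR(1) and 0.02 to 0.1 under compound symmetry.

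**Step 3. Precision**

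Let a fraction d drop out between Day 60 and Day 90. The variance of the Day-90 mean is proportional to R² + (1−R²)/(1−d), where R² is the share of Day-90 variance explained by the earlier modelled visits.

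- AR(1): R² = ρ⁴ without Day 60 and ρ² with it. At ρ = 0.7 and d = 0.20: 0.240 + 0.760/0.8 = 1.190 against 0.49 + 0.51/0.8 = 1.1275. The SE ratio is √(1.190/1.1275) = 1.027, a loss of 2.7%. Across ρ = 0.5 to 0.9 and d = 5% to 20%, the loss is 0.4% to 2.7%.
- Compound symmetry: R² = kρ²/(1+(k−1)ρ), with k = 4 visits against 5. The loss is under 0.2%.

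**The case against.** **The eGFR list follows the protocol.** Table 8-1 does not mark eGFR at Day 60, so the pooled list is the set of on-treatment visits with scheduled eGFR in both parts, and FAS2 adds the visits that only Part 2 has. This is probably the reason, although the SAP does not say so. A reader might infer that the SAP contradicts the eGFR schedule; it does not. But the explanation fails for serum creatinine, a separate endpoint scheduled at Day 60 in both parts. Nor does it require dropping Part 2 Day-60 eGFR, because an MMRM accepts patients with different observed visits.

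**Day 60 is not lost to the report.** A reader might infer that these values are ignored altogether. They are not. SAP 8.2 lists and summarises laboratory data by visit, SAP 8.3 plots them, the safety outputs are re-run after database lock, and the FAS2 models use Day 60. The eGFR model outputs named for the final first interpretable results (SAP section 2) are the FAS2 ones. The omission is confined to the pooled MMRMs.

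**The bias scenario is harsh.** It puts all of the dropout in one arm, within one 30-day window, among exactly the lowest Day-60 values. The allowance of up to 20% in Protocol 11.7 covers all Part 1 dropout. With 48 + about 50 patients over five roughly equal groups, an arm has about 20, so 10% to 20% is 2 to 4 people. Those who stop before Day 60 are unaffected. This objection stands: the upper values are near a worst case. A cruder calculation with Days 30, 60 and 90 only can reach about 1.5 mL/min, but that is not the SAP's model.

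**The analysis is declared final at IA2.** This also stands, and it limits the form of the remedy.

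**Conclusion.** The omission is real and limited to two pooled secondary models. For serum creatinine it has no visible reason. For eGFR it has a probable but unstated one, which does not cover the Part 2 values.

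If dropout between Day 60 and Day 90 depends on the Day-60 value, a decline in renal function can be understated. A reader might infer that a harmful effect is in fact understated here; the documents do not support that, since they give no dropout pattern by Day-60 value.

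Under the assumed SD, correlations and extreme selection, the bias is about 0.1 to 1.3 mL/min. The result turns mainly on the correlation structure, and the SD and correlations are assumptions, not figures from the documents. Bias is the argument here, not precision. The primary UPCR analysis, its error rate and the sample size do not depend on this point.

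**What to change.** In SAP 7.2.1, add Day 60 to the pooled (FAS to Day 90) visit list for serum creatinine and eGFR, and state that Part 1 Day-60 eGFR is calculated from the Day-60 chemistry creatinine with the CKD-EPI equation.

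If the IA2 results already stand as final, leave them unchanged. Run the version with Day 60 as a labelled sensitivity analysis at final database lock, specified in the SAP before the lock, and report it beside the IA2 estimates.

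Cost: no new data collection, but a SAP edit and a repeat of two models. The statistical downside is one more visit in the unstructured covariance of each, which goes from five post-baseline visits to six, or from 5×6/2 = 15 to 6×7/2 = 21 parameters. With about 98 patients this makes convergence somewhat harder. SAP 7.2.3 already names simpler structures to fall back on.

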7.2.2 Descriptive analyses

Secondary variables (raw and change or ratio to baseline depending on the corresponding parameter) will be listed by treatment group, patient and visit/time, and descriptive statistics will be provided by treatment and visit/time, except from hematuria. Summary statistics will include mean (arithmetic and geometric), SD, CV (arithmetic and geometric), Q1, median, Q3, minimum and maximum as appropriate. For parameters that will be analyzed as change from baseline, geometric means and CV will not be provided in the summaries.

A shift table of changes from baseline in hematuria levels will be provided, considering the following three levels: <9rbc/hpf, ≥ 9 rbc/hpf to ≤ 50 rbc/hpf and >50 rbc/hpf, for the FAS (up to Day 90) and FAS2 separately. In addition, a frequency table of hematuria levels will be also produced separately for FAS (up to Day 90) and FAS2.

7.2.3 Statistical model, assumptions and hypotheses

Secondary Variables - MMRM

For each secondary variable (apart from hematuria), a similar statistical model will be used as described for the primary variable, in [Section 7.1.3](#). Each MMRM will have treatment, timepoint (as study day to start of study treatment), study part (Part 1 or Part 2) and ancestry (Asian/non-Asian) as fixed effects, treatment*timepoint and timepoint*baseline as interaction terms and baseline of the dependent variable as fixed covariate. Timepoint will be also included as a repeated factor with an unstructured residual covariance matrix to allow adjustment for correlations between timepoints within subject; if not possible, other appropriate covariance structures will be explored, such as Autoregressive (AR(1)) and Compound symmetry. Where log transformation is used for the dependent variables, log baseline will be used in lieu of baseline in the model covariates and the estimates will be back transformed from the log scale.

For all secondary variables (except hematuria), the MMRM will be repeated considering measurements up to day 180 (i.e. for FAS2 only); the MMRM for this analysis will not include the study part fixed effect term.

UPCR FMV – MMRM

As a supportive analysis, an MCP-Mod test will be also performed for the UPCR (based on FMV samples) for Parts 1 and 2 to Day 90, similar to the analysis described in Section 7.1.3.

[figure not shown]
A further secondary analysis of UPCR (based on the FMV samples) after the end of treatment will be performed for FAS1 and FAS2 separately. This analysis would also follow the MMRM approach described for the primary variable but will include all UPCR measurements up to the EoS visit.

[figure not shown]
Model estimated means and their differences versus placebo (and its 80% CI) will be calculated for each dose level, for all secondary parameter MMRM analyses. These will be back transformed to the original scale to give a geometric mean ratio (and its 80% CI) between each dose and placebo. Graphical methods will be used to present the model estimated means by treatment group and time.

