2.2 Secondary objective(s)

Secondary objective(s)	Endpoints related to secondary objective(s)
To evaluate the safety and tolerability of LNP023	Assessment of safety based on vital signs, physical examination, ECGs, laboratory assessments, and collection of AEs assessed from baseline until the end of the study visit.
To assess the effect of LNP023 on renal function up to 90 days of treatment (combining Part 1 and Part2 of the study)	Estimated glomerular filtration rate (eGFR; estimated by the Chronic Kidney Disease Epidemiology Collaboration (CKD-EPI) equation) Serum creatinine Hematuria (number of erythrocytes/high-power-field (hpf) measured through microscopic examination) 24h-UP, 24h-UA, UACR (urine albumin to creatinine concentration ratio) UPCR (urine protein to creatinine concentration ratio) from first morning void.
To assess the pharmacokinetics of LNP023	Plasma: Non-compartmental parameters related to total parent drug, including but not limited to Tmax, Cmax, AUClast and AUCtau will be calculated for each dose level. Urine: Non-compartmental parameters, including but not limited to total cumulative urinary excretion (Ae) and renal plasma clearance (CLr)
To assess the effect of LNP023 on alternative complement pathway	Plasma levels of alternative pathway biomarkers including Bb and sC5b-9
To estimate the lowest dose that provides maximal reduction of proteinuria	Ratio to baseline of UPCR

Secondary objective(s)	Endpoints related to secondary objective(s)
To assess the effect of LNP023 on renal function up to Day 180 (Part 2 of the study)	Estimated glomerular filtration rate (eGFR; estimated by the Chronic Kidney Disease Epidemiology Collaboration (CKD-EPI) equation) UPCR from 24 hour sample and first morning void Hematuria (number of erythrocytes/high-power-field (hpf) measured through microscopic examination) UACR (urine albumin to creatinine concentration ratio).

3 Investigational plan

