11.5 Analysis of secondary variable(s)

11.5.1 Efficacy / Pharmacodynamics

The secondary variables supporting the secondary objective to assess the effect of LNP023 on renal function are eGFR, serum creatinine, hematuria, 24h-UP, 24h-UA, UACR,, UPCR (from first morning void). These variables will each be analyzed with the same MMRM model used for the primary variable. Appropriate transformations for each variable will be detailed in the SAP. Estimates of the differences between each dose of LNP023 and placebo will be calculated.

For eGFR, UPCR (from 24 hour sample and first morning void), hematuria and UACR, the MMRM will be repeated considering measurements up to day 180 (i.e. for FAS2 only); the MMRM for this analysis will not include the study part fixed effect term.

A further secondary analysis of UPCR after the end of treatment will be performed, for FAS1 and FAS2 separately. This analysis would also follow the MMRM approach described for the primary variable but will include UPCR measured up to the EOS.

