The biomarker data in Table 10 will be listed by treatment, patient, and visit/timepoint. Summary statistics will be provided by treatment and visit/timepoint. The effect of LNP023 treatment on biomarkers, will be explored graphically to show the percent change from baseline concentration plots based on geometric mean (i.e. calculated by back-transforming the mean of the log- transformed ratio to baseline values) and presented as a percentage (e.g. a geometric mean ratio to baseline value of 1.2 will be presented as 20% in the plot, whereas a geometric mean ratio to baseline value of 0.8 will be presented as -20%) over time/visit by treatment group. Additional plots may be used to further explore other relationships.

Biomarkers measured in urine will be analyzed both raw and normalized to urine creatinine levels. Normalization will be performed as the ratio of each biomarker to creatinine value.

Handling of LLOQ and ULOQ

Biomarker data are reported as concentration results, measured using a specific assay with a working range defined by the two following limits: Lower limit of quantification (LLOQ) and Upper limit of quantification (ULOQ). Values which fall below the LLOQ or above the ULOQ are reported as < LLOQ * dilution factor (dilution factor: if sample diluted and concentration measured still below LLOQ) and > ULOQ * dilution factor, respectively.

To ensure that biomarkers only have numerical values, censored values will be imputed as follows

- Values below the LLOQ are replaced by LLOQ*dilution factor/2.
- Values above the ULOQ are replaced by ULOQ*dilution factor.

Imputed values are used for summary statistics, inferential analyses and plots (with a special symbol). Values below LLOQ and values above ULOQ are shown as such in the listings. In the summary table, the frequency (n, %) of values below the LLOQ and above the ULOQ, respectively, will be included.

If the proportion of imputed data is more than 20% for any treatment group at any time point, a footnote is added to the summary statistics table stating that the proportion of values outside the limits of quantification is more than 20% for some treatment groups at some time points, and that in such cases summary statistics may be heavily biased.

11 Considerations due to COVID-19

Due to the COVID-19 pandemic it was not possible to perform some procedures as per protocol. All deviations due to COVID-19 will be listed along with other Protocol deviations and may also be tabulated.

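### The SAP drops the protocol's placebo-comparative model for hematuria and, in its visible text, specifies no placebo contrast for plasma Bb and sC5b-9, although 100 mg was studied only in Part 2

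*SAP*

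**What the plan says.** **Hematuria, protocol.** Section 11.5.1 names the secondary variables for "renal function are eGFR, serum creatinine, hematuria, 24h-UP, 24h-UA", UACR and first-morning-void UPCR. It then says: "These variables will each be analyzed with the same MMRM model used for the primary variable". It adds: "Estimates of the differences between each dose of LNP023 and placebo will be calculated". For the longer treatment period it again includes hematuria: "hematuria and UACR, the MMRM will be repeated considering measurements up to day 180". What it leaves to the SAP is the choice of transformation.

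**Hematuria, SAP.** Section 7.2.3 excludes hematuria from the Day 90 models ("For each secondary variable (apart from hematuria), a similar statistical model will be used as described for the primary variable") and from the Day 180 models ("For all secondary variables (except hematuria), the MMRM will be repeated considering measurements up to day 180"). Section 7.2.2 provides a shift table on three ordered levels and a frequency table, for the FAS to Day 90 and for FAS2. Section 3 likewise omits confidence intervals for hematuria at the first interim analysis.

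**Complement biomarkers.** Protocol 2.2 has a separate secondary objective, "To assess the effect of LNP023 on alternative complement pathway", with plasma Bb and sC5b-9 as its endpoint. SAP Section 10 plans listings, summary statistics by treatment and visit, and this: "The effect of LNP023 treatment on biomarkers, will be explored graphically to show the percent change from baseline concentration plots based on geometric mean". SAP Section 9 adds exposure-response scatterplots and modelling. Section 10 mentions inferential use of imputed values, but the visible text defines no such analysis.

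**The concern.** The SAP should carry out the protocol's analysis or say why it does not. For hematuria it does neither. A reader of the final report will see how patients moved between levels in each arm, but no estimate with an interval for any dose against placebo.

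For Bb and sC5b-9 the stated objective is an effect of the drug, yet the visible plan leaves the reader to compare arms by eye. Exposure-response modelling does not fill this gap, because it does not estimate each randomised dose against placebo.

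The two-part design makes comparison by eye riskier than usual. The 100 mg arm was added after the first interim analysis, so none of its patients was randomised alongside Part 1 placebo. The pooled MMRMs for the other variables contain a study-part term. The pooled displays for hematuria and the biomarkers do not.

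**Working it through.** No sample size, power or interval in the plan is in dispute, so there is no stated figure to reproduce. The check compares the texts and then sizes the part imbalance.

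**Texts side by side**

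| Endpoint | Protocol | Visible SAP |
|---|---|---|
| Hematuria to Day 90 | 11.5.1: primary MMRM, each dose against placebo | 7.2.2, 7.2.3: no model; shift and frequency tables |
| Hematuria to Day 180 (FAS2) | 11.5.1: MMRM repeated | 7.2.3: excluded; same tables in FAS2 |
| Plasma Bb, sC5b-9 | 2.2: endpoint of a secondary objective; not listed in 11.5.1 | 9, 10: listings, summaries, plots, PK/PD; no placebo contrast |

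**Inputs**
- Part 1 allocation: placebo 14, 10 mg 10, 50 mg 10, 200 mg 14; no 100 mg arm (Protocol 3.1).
- Part 2: about 50 patients, five arms including 100 mg, aiming for roughly equal arms over both parts (Protocol 3.1).
- Two-sided 80% intervals for efficacy (Protocol 11.4), multiplier 1.2816.

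**Step 1: arm sizes.** (48 + 50)/5 = 19.6 per arm. The Part 2 numbers are then placebo 5.6, 10 mg 9.6, 50 mg 9.6, 100 mg 19.6 and 200 mg 5.6. Placebo from Part 1: 14/19.6 = 71%. With 48 in Part 2 it is 14/19.2 = 73%.

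**Step 2: leakage of a part difference.** Let the change from baseline differ by x between parts. A raw pooled comparison with placebo carries x times the difference in Part 2 shares:
- 100 mg: 1 − 5.6/19.6 = 0.71
- 10 and 50 mg: 9.6/19.6 − 5.6/19.6 = 0.20
- 200 mg: 0

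**Step 3: what adjustment costs in precision.** Four arms exist in both parts and identify an additive part effect. Each contributes information n1·n2/(n1 + n2):
- placebo and 200 mg: 14 × 5.6/19.6 = 4.00 each
- 10 and 50 mg: 10 × 9.6/19.6 = 4.90 each

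The total is 17.8, so the variance of the part effect is 1/17.8 = 0.056 (in SD² units). For 100 mg versus placebo:

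variance = 2/19.6 + 0.714² × 0.056 = 0.102 + 0.029 = 0.131; SE = 0.362 SD; half-width = 1.2816 × 0.362 = 0.46 SD.

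| 100 mg versus placebo | 80% half-width, Part 2 = 50 | Part 2 = 48 |
|---|---|---|
| Raw pooled (carries 0.71x) | 0.41 SD | 0.41 SD |
| Adjusted for part | 0.46 SD | 0.47 SD |
| Part 2 patients only | 0.61 SD | 0.63 SD |

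**Step 4: log scale for the biomarkers.** The documents give no SD for the log ratio to baseline. Assuming 0.3, the adjusted half-width is 0.46 × 0.3 = 0.14. For SDs of 0.2 to 0.5 it is 0.09 to 0.23. These figures take every randomised patient as measured. Protocol 8.5.2 restricts the assay to selected sites, so the true intervals will be wider.

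**The case against.** - **A Gaussian MMRM suits hematuria poorly.** Microscopy follows only a positive dipstick (Protocol 8.6.3), and the SAP works with three ordered levels. This stands as a reason to change the model. It is not a reason to have no dose-placebo estimate, and the SAP does not offer it.
- **Descriptive biomarker reporting is acceptable in Phase II.** Protocol 8.5.2 treats these as mode-of-action markers, and 11.5.1 promises no contrast for them. A reader might infer a second protocol-SAP conflict. The documents do not support that. Protocol Section 11.6 is not in the supplied text and parts of the SAP are redacted, so a biomarker model elsewhere cannot be excluded. The point stands only as a gap in what can be read.
- **The part imbalance may be harmless.** Nothing in the documents shows that change from baseline differs between parts, and the imbalance matters mainly for one dose of four. The FAS2 displays lie wholly within Part 2 and avoid it. All this limits the size of the problem, but FAS2 has at most about 5 to 6 placebo patients.
- **Selected-site sampling.** A reader might infer bias. The text does not say that site choice depends on arm, so the supported consequence is fewer patients.
- **A Day 180 hematuria model is not workable.** Two thresholds, four treatment terms, one for ancestry and two for baseline level make nine parameters on at most about 50 patients, with 5 to 6 on placebo. This stands, and the fix leaves Day 180 descriptive.

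**Conclusion.** The hematuria discrepancy is certain from the text: the protocol promises a dose-placebo estimate at both horizons, and the SAP withdraws it without a visible reason. The biomarker gap is certain only for the visible SAP.

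Two stronger readings should be resisted. First, it is not the case that two secondary objectives lose their placebo comparison. The renal-function objective keeps MMRM estimates for eGFR, serum creatinine, 24h-UP, 24h-UA, UACR and UPCR, and loses one for hematuria alone. Only the complement objective is left without any specified contrast. Second, the biomarkers do not get plots alone; summary statistics, listings and PK/PD modelling are planned too.

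The size of the part problem is 0.71 of an unknown part difference for 100 mg, about 0.20 for 10 and 50 mg, and none for 200 mg. This assumes about 50 patients in Part 2 and equal arms overall. Adjustment removes it if the part effect is additive, and widens the 80% half-width only from 0.41 to 0.46 SD at full enrolment. The point is worth correcting, but it does not touch the primary analysis.

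**What to change.** 1. **Plasma Bb and sC5b-9.** In SAP Section 10, specify the 7.2.3 MMRM on the log ratio to baseline to Day 90: treatment, visit, part, ancestry, log baseline, and the visit interactions with treatment and log baseline. Report geometric mean ratios to placebo with 80% confidence intervals and the number measured per arm and part.
2. **Hematuria at Day 90.** Reconcile SAP 7.2.3 with Protocol 11.5.1 by adding an ordinal model on the SAP's three levels in the pooled FAS, with treatment, part, ancestry and baseline level. Merge levels by a rule set in advance if cells are sparse. State how a visit with a negative dipstick and no microscopy is classed. Report odds ratios to placebo with 80% confidence intervals.
3. **Hematuria at Day 180.** Keep the FAS2 tables descriptive and record why the protocol's model is not fitted.
4. Keep the existing tables and plots, and note on the pooled displays that 100 mg comes from Part 2 only.

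The cost is SAP wording and a few model runs on data already collected. The hematuria odds ratios will be imprecise and should be presented as such.
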